3.6 RAI ABLATIVE TREATMENT

Activity of 131-I will be determined by dosimetry performed during diagnostic study. The therapeutic dose will not exceed 600 miCu.

3.7 RESEARCH EVALUATIONS

3.7.1 Tumor tissue biopsy samples

3.7.1.1 Patients who have locoregional or metastatic disease that is amenable to ultrasound guided and or CT scan guided needle biopsy will have this done of the target lesion. This will be performed at study entry and at week 10.

3.7.1.2 These samples will be processed as described in Section 5.4.

3.8 FOLLOW UP FOR ALL PATIENTS {FROM WEEK 17}

- 3 months
 - Physical exam including ECOG status
 - CBC with differential, platelets, BUN, creatinine, total protein, total bilirubin, ALT, AST, ALKP, amylase, ammonia, albumin.
 - CT and/or MRI of the chest
 - Health Related Quality of Life HRQOL) form completion
 - Ultrasound of the neck as indicated
 - Tg, TSH
- 6 months
 - Physical exam including ECOG status
 - CBC with differential, platelets, BUN, creatinine, total protein, total bilirubin, ALT, AST, ALKP, amylase, ammonia, albumin..
 - Tg, TSH
 - Health Related Quality of Life HRQOL) form completion
- 9 months - for patients continuing on valproic acid only-
 - Physical exam including ECOG status
 - CBC with differential, platelets, BUN, creatinine, total protein, total bilirubin, ALT, AST, ALKP, amylase, ammonia, albumin.
 - Tg, TSH
 - Health Related Quality of Life HRQOL) form completion

- 12 months
 - Physical exam including ECOG status
 - CBC with differential, platelets, BUN, creatinine, total protein, total bilirubin, ALT, AST, ALKP, amylase, ammonia, albumin.
 - CT and/or MRI of the chest
 - Ultrasound of the and neck
 - Tg, TSH
 - Health Related Quality of Life HRQOL) form completion

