2.1.2 Exclusion Criteria

2.1.2.1 Allergy to valproic acid.

2.1.2.2 Current coexisting malignancy other than basal cell carcinoma.

2.1.2.3 Women of child-bearing potential who are pregnant or breastfeeding. Valproic acid is a known teratogen, causing primary neural tube defects, facial abnormalities, and skeletal malformation; therefore pregnant women will be excluded. Additionally, patients that become pregnant while on study protocol will be discontinued immediately.

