3 STUDY IMPLEMENTATION

3.1 STUDY DESIGN

Current conventional therapy for patients with thyroid cancers of follicular cell origin after thyroidectomy and ablative treatment with 131-I involves only thyroid hormone for TSH suppression. In this study, patients will receive TSH suppression therapy with valproic acid for 16 weeks.

The total study period will be 18 weeks, with a one year follow up. Patients who respond to treatment as evidenced by decreased Tg level, RAI uptake or decreased tumor size will continue treatment of valproic acid for 1 year.

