3.3 EVALUATIONS WEEKS 1-10 {ALL EVALUATIONS ARE +/- 3 DAYS}

- Week 2-10:
 - Serum valproic acid levels may be performed weekly on all patients for at least the first 4 weeks of treatment.
 - Reports from all evaluations performed at outside institutions will be faxed to:

[name] or [name]
[contact]

This includes lab values, physical exams, patient diaries, etc.

- Week 2 (Day 10):
 - Physical exam including ECOG status
 - CBC with differential, platelets, BUN, creatinine, total protein, total bilirubin, ALT, AST, ALKP, amylase, ammonia, albumin and b-HCG (if applicable).
 - Toxicity assessment, pill count, and review of diary
- Week 4 – may be performed by their primary physicians
 - Physical exam including ECOG status
 - CBC with differential, platelets, BUN, creatinine, total protein, total bilirubin, ALT, AST, ALKP, amylase, ammonia, albumin and b-HCG (if applicable).
 - Toxicity assessment, pill count, and review of diary

- Week 6:
 - Physical exam including ECOG status
 - CBC with differential, platelets, BUN, creatinine, total protein, total bilirubin, ALT, AST, ALKP, amylase, ammonia, albumin and b-HCG (if applicable).
 - Toxicity assessment, pill count, and review of diary
- Week 8 - may be performed by their primary physicians
 - Physical exam including ECOG status
 - CBC with differential, platelets, BUN, creatinine, total protein, total bilirubin, ALT, AST, ALKP, amylase, ammonia, albumin and b-HCG (if applicable).
 - Toxicity assessment, pill count, and review of diary
- Week 10:
 - Physical exam including ECOG status
 - CBC with differential, platelets, BUN, creatinine, total protein, total bilirubin, ALT, AST, ALKP, amylase, ammonia, albumin and b-HCG (if applicable).
 - Serum valproic acid levels.
 - Toxicity assessment, pill count, and review of diary
 - Tg, TSH
 - Thyrogen Scan
 - Health Related Quality of Life HRQOL) form completion
 - Tumor tissue biopsy of any accessible lesions (Section 3.7)
 - 24 hour urinary iodine level

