3.5 PHASE 2 WEEKS 11-16

3.5.1 Schedule 1 - Patients who exhibit an increased radioiodine uptake on Thyrogen scan post valproic acid therapy at week 10.

- Week 11:
 - Discontinue Levothyroxine
 - Begin Cytomel for 4 weeks (25 micrograms twice a day)
 - Continue valproic acid for a total of 16 weeks

Note: medication will be dispensed following review of Thyrogen scan
- Week 12 - may be performed by their primary physicians
 - Physical exam including ECOG status
 - CBC with differential, platelets, BUN, creatinine, total protein, total bilirubin, ALT, AST, ALKP, amylase, ammonia, albumin and b-HCG (if applicable).
 - Toxicity assessment, pill count, and review of diary
- Week 14: may be performed by their primary physicians
 - Physical exam including ECOG status
 - CBC with differential, platelets, BUN, creatinine, total protein, total bilirubin, ALT, AST, ALKP, amylase, ammonia, albumin and b-HCG (if applicable).
 - Toxicity assessment, pill count, and review of diary
 - Stop Taking Cytomel.
 - Begin low iodine diet.
- Week 16:
 - Measure TSH, Tg and 24 hour urinary iodine.
 - I-131 Ablative treatment {refer to Section 3.6}.
 - Physical exam including ECOG status
 - CBC with differential, platelets, BUN, creatinine, total protein, total bilirubin, ALT, AST, ALKP, amylase, ammonia, albumin and b-HCG (if applicable).
 - Toxicity assessment, pill count, and review of diary
- Week 17:
 - Post ablation RAI scan {5 days (+/- 2 days) following administration of 131-I}.
 - Ultrasound of the neck
 - MRI or CT of the neck and chest
 - FDG-PET scan
 - Resume Levothyroxine (pre study dose) .

- Stop valproic acid end of week 17
- Toxicity assessment, pill count, and review of diary
- Health Related Quality of Life HRQOL) form completion

3.5.2 Schedule 2 – patients who do not exhibit an increased radioiodine uptake on Thyrogen scan post valproic acid therapy at week 10

- Week 11:
 - Maintain valproic acid dose
- **Note:** medication will be dispensed following review of the Thyrogen scan.
- Week 12:
 - Physical exam including ECOG status
 - CBC with differential, platelets, BUN, creatinine, total protein, total bilirubin, ALT, AST, ALKP, amylase, ammonia, albumin and b-HCG (if applicable).
 - Serum valproic acid levels.
 - Toxicity assessment and review of diary
- Week 14: may be performed by local physician
 - Physical exam including ECOG status

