 - CBC with differential, platelets, BUN, creatinine, total protein, total bilirubin, ALT, AST, ALKP, amylase, ammonia, albumin and b-HCG (if applicable).
 - Toxicity assessment and review of diary
- Week 16:
 - Physical exam including ECOG status
 - CBC with differential, platelets, BUN, creatinine, total protein, total bilirubin, ALT, AST, ALKP, amylase, ammonia, albumin and b-HCG (if applicable).
 - Tg, TSH
 - Toxicity assessment and review of diary
 - Ultrasound of the neck and mediastinum
 - MRI or CT of the neck and chest
 - FDG-PET scan
 - Health Related Quality of Life HRQOL) form completion
- Weeks 17-52
 - Patients who show a response by RECIST criteria or have a decreased thyroglobulin level from Day 1 of the treatment (registered as a partial response to the treatment) will continue on valproic acid at their current dose for a total of 52 weeks.

- Stop valproic acid if no response
- Sixteen weeks or 4 months is significant amount of time to measure response to treatment and therefore, if there is a response, a patient's thyroglobulin levels should have decreased by then, as well as, by RECIST criteria.
- Patients who show no response, patients will stop valproic acid treatment and continue with routine follow up.

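### Patients who stay on valproic acid after week 16 have no scheduled pregnancy test for 36 of 52 weeks, and their scheduled toxicity and diary reviews stop too

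*Protocol*

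**What the plan says.** **Treatment after week 16.** Under section 3.5.2 (weeks 17-52), Schedule 2 patients who respond by RECIST or have a lower thyroglobulin "will continue on valproic acid at their current dose for a total of 52 weeks". For Schedule 1, section 3.5.1 says "Stop valproic acid end of week 17". Section 3.1, however, says that patients who respond "as evidenced by decreased Tg level, RAI uptake or decreased tumor size will continue treatment of valproic acid for 1 year", which would take in Schedule 1 patients as well.

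**Monitoring up to week 16.** At weeks 2 to 10 (section 3.3) each visit has b-HCG, if applicable, on the laboratory line, together with "Toxicity assessment, pill count, and review of diary". Schedule 1 keeps these items at weeks 12, 14 and 16. Schedule 2 also keeps the test at those weeks, its laboratory line ending "amylase, ammonia, albumin and b-HCG (if applicable", and lists "Toxicity assessment and review of diary" without a pill count.

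**Monitoring from week 17.** Section 3.8 lists visits at 3, 6, 9 and 12 months, the third being "9 months - for patients continuing on valproic acid only". All four keep the physical examination, CBC, chemistry panel, Tg and TSH, and the quality-of-life form. The chemistry panel is the one used before, except that it ends at albumin. No visit lists b-HCG, a toxicity assessment, a diary review or a pill count.

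**Pregnancy rules.** Section 2.1.2.3 identifies valproic acid as a teratogen and states that "patients that become pregnant while on study protocol will be discontinued immediately". Section 3.9.1 makes pregnancy a reason for removal from therapy. Section 2.1.1.11 requires contraception during treatment and for three months afterwards.

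**The concern.** Section 3.8 reads like an off-treatment follow-up list that has also been applied to patients still taking the drug. The dose does not change after week 16 and neither does the fetal hazard, but the scheduled check for pregnancy goes from every two weeks to never, and no reason is given.

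The main stake is participant safety. Immediate discontinuation in pregnancy can be acted on only once a pregnancy is known, and after week 16 nothing on the schedule would reveal one. Contraception remains the primary control. The test is the check on it, and the protocol evidently thought that check necessary for the first 16 weeks.

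A secondary stake is symptomatic toxicity. Section 9.1.6 lists somnolence, nausea and vomiting, which laboratory tests do not show. Without a scheduled assessment, their capture becomes less systematic. Patients are taught to keep a diary (section 3.2.1), but from week 17 no visit calls for anyone to look at it.

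**Working it through.** The protocol states no figure to reproduce. The check compares the visit lists and counts weeks.

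**Step 1: visits that list each item for a Schedule 2 continuer**

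| Item | Weeks 2, 4, 6, 8, 10 (3.3) | Weeks 12, 14, 16 (3.5.2) | Months 3, 6, 9, 12 (3.8) |
|---|---|---|---|
| b-HCG (if applicable) | 5 of 5 | 3 of 3 | 0 of 4 |
| Toxicity assessment | 5 of 5 | 3 of 3 | 0 of 4 |
| Diary review | 5 of 5 | 3 of 3 | 0 of 4 |
| Pill count | 5 of 5 | 0 of 3 | 0 of 4 |

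So 5 + 3 = 8 visits, one every two weeks, carry the pregnancy test up to week 16, and none does afterwards. The count of 8 is the same on Schedule 1. The pill count had already left the Schedule 2 lists by week 12; the last one implied is with the week 12 trough level (section 3.2.2). Section 3.8 therefore does not newly drop it.

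**Step 2: time on drug without a scheduled test**

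- Total treatment: 52 weeks (section 3.5.2). Last listed test: week 16.
- Untested time on drug = 52 − 16 = 36 weeks.
- Share of treatment = 36/52 = 0.69, or 69%.

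**Step 3: where the section 3.8 visits fall**

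The protocol does not fix the origin of the months, so both readings are shown, with 3 months taken as 13 weeks.

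- *From week 17:* 17 + 13 = 30, 17 + 26 = 43, 17 + 39 = 56, 17 + 52 = 69. Two visits (weeks 30 and 43) are on drug.
- *From treatment start:* weeks 13, 26, 39 and 52. Three visits lie after week 16 and no later than week 52.

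Neither reading fits perfectly. The first agrees with the section title, but it puts the visit reserved for patients on drug at week 56, after the drug ends. The second puts the 3-month visit at week 13, before the section begins. The missing test is the same either way.

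**Step 4: longest untested interval if those visits carried the test**

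- *From week 17:* 30 − 16 = 14, 43 − 30 = 13, 52 − 43 = 9. Longest: 14 weeks.
- *From treatment start:* 26 − 16 = 10, 39 − 26 = 13, 52 − 39 = 13. Longest: 13 weeks.

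Both compare with 36 weeks as written.

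**The case against.** The strongest case against is that most of the safety net stays in place and that the point should be narrowed to the pregnancy test.

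- **Toxicity.** Section 8.3 promises careful evaluation of toxicity, weekly team discussion of adverse events and quarterly review by the principal investigator, none of it limited to the first 16 weeks. Section 5.1.1 narrows event capture only from 30 days after the last treatment. The stopping rule in section 3.2.4 runs through treatment and follow-up. The section 3.8 blood tests cover the removal thresholds for liver enzymes, platelets, ammonia and amylase. This stands: what is lost is a scheduled assessment, not adverse event recording, so the toxicity part is secondary.
- **Pill count.** It was already absent from the Schedule 2 lists, so asking for it adds a requirement. This also stands.
- **Affected group.** It consists of women of childbearing potential among those who continue, in a trial of at most 25 patients, with contraception mandated. That limits the expected number of events but leaves the rule on discontinuation without a scheduled means of detection.
- **Remaining gap.** Tests 13 to 14 weeks apart would still find a pregnancy late. True, but this is an argument for testing more often, not for no testing.
- **Documents not seen.** The study schema (Appendix 1) is not in the text at hand and might list the test. If it does, the section 3.8 lists would still need to be aligned with it.

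None of these points supplies a pregnancy test after week 16. The mention of b-HCG in section 5.1.1 governs which outside laboratory values are captured, not when a test is done.

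**Conclusion.** The point holds. As written, a patient who continues has no scheduled pregnancy test for 36 of 52 treatment weeks (69%), after eight two-weekly tests, where applicable, up to week 16. The scheduled toxicity assessment and diary review end at the same time. These are a lesser matter because other adverse event recording, examinations and safety laboratory tests go on.

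The conclusion rests on the visit lists in the protocol text, without Appendix 1. It applies with certainty to Schedule 2 responders. It extends to Schedule 1 only if section 3.1 prevails over section 3.5.1. The protocol gives neither the number of continuers nor the number of women of childbearing potential, so no patient count is claimed. Efficacy inference is untouched: response is judged at weeks 10 and 16, and the Simon decision does not depend on these visits.

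**What to change.** At every section 3.8 visit that falls while the patient is taking valproic acid:

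- add b-HCG (if applicable) to the laboratory line;
- add one line for toxicity assessment, pill count and diary review.

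Leave the contraception requirement (2.1.1.11) and the stopping rule (3.2.4) as they are.

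The cost is one assay where applicable and a few minutes of nurse time at 2 or 3 existing visits per continuing patient. Blood is already drawn at these visits, and section 5.1.1 already lists b-HCG among the outside laboratory values captured. The limitation is that tests about 13 weeks apart detect pregnancy later than the two-weekly tests used before week 16. If the sponsor wants shorter intervals, the protocol already lets a patient's own physician perform some of the visits up to week 14, and tests between the section 3.8 visits could be done the same way.

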3.9 CRITERIA FOR REMOVAL FROM PROTOCOL THERAPY AND OFF STUDY CRITERIA

3.9.1 Criteria for removal from protocol therapy

- Patient request
- PI discretion, if the PI feels it is not in the best interest of the patient to remain on treatment
- Liver Dysfunction (enzyme levels above 1.5 times ULN)
- Platelet < 50,000
- Ammonia levels > 65 mol/l
- Progressive disease
- Pregnancy
- Pancreatitis (amylase level above 1.5 ULN)
- Alcohol consumption
- Other unacceptable toxicities as determined by the PI

3.9.2 Off-study Criteria

- Completion of the follow up period
- Patient request
- PI discretion ,if the PI feels it is not in the best interest of the patient to remain on treatment

Note: Patients must remain on study until all study related adverse events have resolved to grade 2 or less or baseline.

3.9.3 Off-Study Procedure

Authorized staff must notify Central Registration Office (CRO) when a subject is taken off-study. An off-study form from the web site

(<http://home.ccr.cancer.gov/intra/eligibility/welcome.htm>) main page must be completed and faxed to [contact].

4 SUPPORTIVE CARE

Appropriate supportive care for any side effects or toxicity may be provided by the Endocrine Oncology Branch. Patients may be admitted as necessary to manage issues related to study medication or disease process.

5 DATA COLLECTION AND EVALUATION

5.1 DATA COLLECTION

Data will be collected using the NCI C3D web based data collection system. All data will be kept secure. Personal identifiers will not be used when collecting and storing data. An enrollment log will be maintained in the regulatory binder/file which is the only location of personal identifiers with unique subject identification number.

5.1.1 Routine Data Collection

Following enrollment, all adverse events will be described in the source documents and be reviewed by the designated research nurse, and captured in C3D.

- For laboratory values obtained at sites other than the NIH Clinical Center: only the following values (highest grade per cycle) will be captured in C3D:
 - Hemoglobin, total white blood cell count, absolute neutrophil count, platelet count
 - Creatinine, ALT, AST, Total bilirubin, Total protein, Albumin, Alkaline phosphatase, Amylase, Ammonia and b-HCG (+/-) if appropriate.
 - Any unexpected laboratory abnormality \geq grade 2 possibly, probably or definitely related to the research
- During the follow up period (more than 30 days following the last treatment), only those events that are serious, unexpected, and related to the treatment will be captured in C3D.

5.1.2 Exclusions to Routine Data Collection

The following Adverse Events will be captured only in the source documents and will not be reported in C3D:

- Laboratory values that do not support the diagnosis of a reportable event
- All grade 1 events

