3.2.3 Dose Modification

Based on the serum valproic acid trough level, the dose of valproic acid will be titrated as noted below to maintain serum trough levels between 50 and 100 $\mu\text{g}/\text{ml}$. Any change of the dose of valproic acid will require repeat serum trough levels within 3 days as described above.

- If the serum trough level is $> 100 \mu\text{g}/\text{ml}$, the dose will be reduced by 125 to 500 mg depending on the serum level
- If the serum trough level is $< 50 \mu\text{g}/\text{ml}$, the dose will be increased by 125 to 500 mg depending on the serum level
- For persistent grade 2 toxicities, the dose will be adjusted at the discretion of the PI
- For grade 3 or greater toxicities, the dose will be held until the toxicity has resolved to grade 1 or baseline. Following resolution, the dose will be reduced

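### The rule keeping grade 1 events out of C3D makes no exception for an event that ends protocol therapy (minor, cheap to fix)

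*Protocol*

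**What the plan says.** Protocol 5.1.1 sets the general rule that "all adverse events will be described in the source documents and be reviewed by the designated research nurse, and captured in C3D". Protocol 5.1.2 then narrows it. Under the lead-in "The following Adverse Events will be captured only in the source documents and will not be reported in C3D" it lists two classes: laboratory values that do not support a reportable diagnosis, and "All grade 1 events". The second is unconditional, and no exception for an event that ends therapy appears elsewhere in the protocol.

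Protocol 3.9.1 lists the reasons for removal from therapy. One is "Liver Dysfunction (enzyme levels above 1.5 times ULN". Others are the patient's own request, investigator discretion, and other toxicity the investigator finds unacceptable. None of these four is tied to a grade.

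Protocol 5.3 adopts CTCAE 4.0 for grading but prints none of its limits. Protocol 6.1 says toxicities will be tabulated by grade and organ system.

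**The concern.** An event that ends treatment matters for tolerability whatever its grade. Here the decision to remove a patient and the decision to record an adverse event use different yardsticks: a multiple of ULN or a judgement for the first, a CTCAE grade for the second. Where they part, a patient can leave therapy because of a toxicity that never enters the adverse event data.

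At stake is the accuracy of the toxicity table. Hepatotoxicity is the first toxicity listed for the drug in 9.1.6, and a table with no liver event for a patient removed for liver dysfunction would mislead. Planned enrolment is 25 (6.2), so one such patient would be 1/25 = 4% of those enrolled. That shows scale only and is not an expected count.

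**Working it through.** The plan states no figure on this point, so there is none to reproduce. The check sets the recording rule against the removal rules.

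**Liver trigger.** Inputs:
- removal threshold: above 1.5 times ULN (3.9.1);
- entry limit for AST and ALT: below 1.5 times ULN (2.1.1.12), so a patient who meets the removal rule on these enzymes has risen since entry;
- upper limit of grade 1 for AST/ALT, called L: not in the protocol, so an assumption, examined from 1.5 to 5 times ULN.

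A peak value x (in multiples of ULN) triggers removal if x > 1.5 and is excluded from C3D as grade 1 if x ≤ L. Both hold when 1.5 < x ≤ L, a band of width L − 1.5 when L exceeds 1.5, and otherwise empty.

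| Assumed L (times ULN) | Peaks that trigger removal but have no adverse event entry | Width (times ULN) |
|---|---|---|
| 1.5 or lower | none | 0 |
| 2 | above 1.5, up to 2 | 2 − 1.5 = 0.5 |
| 2.5 | above 1.5, up to 2.5 | 2.5 − 1.5 = 1.0 |
| 3 | above 1.5, up to 3 | 3 − 1.5 = 1.5 |
| 5 | above 1.5, up to 5 | 5 − 1.5 = 3.5 |

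The gap exists for every L above 1.5 and for no L at or below it. The protocol gives no removal rate, so the width cannot be turned into a number of patients.

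**Triggers without a threshold.** Patient request, investigator discretion and investigator-judged toxicity need no assumption about L. Nausea and somnolence are both listed in 9.1.6. A patient with persistent grade 1 nausea may ask to stop. 3.9.1 then permits removal, and 5.1.2 keeps the nausea out of C3D.

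**Does the event count as an adverse event?** Protocol 8.1.1 includes symptoms reported by the patient and clinically significant laboratory findings. A laboratory change that ends therapy is hard to call anything else.

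**Dose changes.** The same gap does not arise for toxicity-driven dose changes, because 3.2.3 starts them at grade 2: "For persistent grade 2 toxicities, the dose will be adjusted at the discretion of the PI". An exception confined to removal is therefore enough.

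**After the fix.** With removal-causing events exempt from 5.1.2, the band is empty for any L and the judgement-based removals are covered too.

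**The case against.** The strongest reply is that nothing here is wrong. 5.1.2 is a declared limit under its own heading, and leaving minor events out of a small phase II database is legitimate. This stands: 5.1.1 and 5.1.2 do not contradict each other, and the general exclusion is not criticised. What remains is that the rule, followed as written, has a poor result in one identifiable situation.

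A second reply is that the liver case depends on a limit the protocol does not print, and that the range examined includes no gap at all. This also stands, and the liver case is conditional for that reason. The judgement-based triggers do not share the condition.

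A third reply is that the removal is recorded anyway. The event stays in the source documents. For laboratory results from outside sites, 5.1.1 says "only the following values (highest grade per cycle) will be captured in C3D", and AST and ALT are on that list with no grade 2 floor. Protocol 8.3 names an Off Treatment e-CRF and has adverse events discussed weekly. This largely stands. The fields of the Off Treatment form are not shown, and it may already give the reason for removal. A reader might infer that such removals vanish from the trial's records, but the protocol does not support that. What is missing is the graded adverse event entry from which a toxicity table is normally built.

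A fourth reply is that the layout of the 6.1 table belongs to the statistical analysis plan, which is not at hand. For the layout this is fair. But that plan cannot draw from the adverse event data an entry that the protocol has kept out of them.

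Two further inferences should be resisted. One is that 5.1.2 removes these events from the continuing-review summary. Protocol 8.2.2 leaves out grade 1 on its own terms, and amending 5.1.2 would not change that. The other is to measure the loss by the share of scheduled blood panels that may be done by outside physicians. That share describes where blood is drawn and says nothing about how many adverse event entries are missing.

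**Conclusion.** The point holds as a minor one. 5.1.2 as written can leave a toxicity that ended protocol therapy without an adverse event entry in C3D, and so possibly out of the 6.1 table. For the judgement-based triggers this follows from the text alone. For the liver trigger it holds only if the CTCAE 4.0 grade 1 limit for AST/ALT is above 1.5 times ULN, which is assumed. The number of patients affected is unknown and may be zero.

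No claim is made about the platelet, ammonia or amylase triggers, whose grades the protocol does not print either. A reader might also fear for the main conclusions of the trial, but these are untouched: response does not use adverse event data, the Simon boundaries do not change, and the stopping rule in 3.2.4 concerns withdrawals for grade 3 toxicity.

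**What to change.** Amend the second exclusion in 5.1.2 to read: *All grade 1 events, except any event that leads to removal from protocol therapy (3.9.1), which is captured in C3D as an adverse event.*

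In the toxicity table under 6.1, show removal-causing events of any grade in a separately labelled line. State that other grade 1 events are not included.

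The cost is one clause and one sentence, using information already held in the source documents. The downside is a few more e-CRF entries and a grade 1 count that is partial and must be labelled so.
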